4.2.1. Analysis Specifications

All efficacy analyses will be analyzed in the ITT-i set (except for the primary endpoints and selected secondary endpoint which will also be analyzed on the ITT and PP Sets) and will be tabulated per treatment group for each stratum separately (region and age) and per treatment group overall (over all strata).

4.2.1.1. Level of Significance

The primary hypothesis is a positive dose-response relationship for the AUC of active treatment regimens. The positive dose-response relationship assumes that dose regimens with higher exposure with respect to MD will have at least an equal or better effect on viral load. Therefore 2 contrasts will be tested at each of the interim analysis points and final analysis; a contrast with no difference between the 2 active regimens tested against placebo and a contrast with a positive linear dose-response relationship with respect to active regimens. With respect to multiple contrast testing, multiplicity will be controlled at the prespecified (interim) alpha level by calculating adjusted p-values from the simulated distribution of the maximum or maximum absolute value of a multivariate t random vector (ie, using the correlation between the contrasts to optimally control for alpha)¹. The overall (family-wise) type 1 error rate of 2.5% (1-sided) will be adjusted for multiple testing due to formal interim analyses using an O'Brien-Fleming alpha spending function with 3 sequential tests (2 interim, 1 final)⁵.

4.2.2. Data Handling Rules

For analysis purposes the log₁₀ qRT-PCR viral load will be imputed with 0 when the result is 'negative', and the midpoint on the log scale between the limit of detection and limit of quantification when the result is 'positive' but non-quantifiable.

4.2.3. Primary Efficacy Endpoint

4.2.3.1. Definition

The primary estimates of the AUC will be derived from a mixed model (see section 4.2.3.2 for the detailed specification). No imputations of missing data from nasal swabs post-baseline will be done in this model, as this mixed model would allow to make inferences under the *missing at random* assumption.

Note that for the primary endpoint the following rules apply:

- Only values as provided by the central lab will be used.
- Baseline (Day 1) is defined as the last measurement before first intake. In case a result is available that is no later than 1 hour after treatment initiation this may be used but only if no pre-treatment observation is available.
- If for the baseline assessment the central laboratory value is missing, the value that will be imputed is based on the average value as based on the analysis population (ITT-i, ITT or PP population).
- For all post-baseline days the RSV RNA viral load result of the swab that was performed at that day will be used, counting from the Day of first treatment which is defined as Day 1.
- In case multiple nasal swabs were taken on a single day the average on the log scale will be used as the value for that subject.

As a sensitivity analysis, descriptive statistics will be provided for the viral load AUC calculated by the trapezoidal summation rule, based on planned days of sampling (Baseline visit up till/including Day 7 visit, or up to 11 days if the dose duration is extended to up to 10 days), including the timepoints with (imputed) values available:

$$AUC_{0-7 \text{ days}} = \frac{1}{2} \sum_{i=1}^n (y_i + y_{i-1}) \times (t_i - t_{i-1})$$

where $i=1,2,3,\dots,n$ are the time points when post baseline samples are collected, y_i is the log 10 viral load at the time and t_i is the time in hours post baseline. y_0 is the baseline log 10 viral load. t_0 is time 0.

The following additional rules, on top of the rules of the primary analysis, will be applied to deal with missing values post-baseline before calculating the Viral load AUC:

- Missing value between baseline and day 7 will be imputed by intrapolation.
- If the last observations are missing, the last available observation will be carried forward. Unscheduled assessments will be included and will be eligible for carrying forward.

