 - s. The mid-turbinate nasal swab (if non-intubated) or endotracheal sample (if intubated) taken during screening is placed in 3 mL of transport media and split into several aliquots, which are used to confirm RSV infection locally and centrally, and to assess for viral and bacterial co-infection centrally. From Day 1 to Day 7 and on Day 10, Day 14, and Day 28, 1 mid-turbinate nasal swab (if non-intubated) or 1 mid-turbinate nasal swab and 1 endotracheal sample (if intubated) will be taken per day to assess RSV RNA viral load and resistance and in some cases to assess the infectious virus yields using a plaque assay. Should the study drug duration be increased to up to 10 days (following review of the data by the IDMC), 1 mid-turbinate nasal swab (if non-intubated) or 1 mid-turbinate nasal swab and 1 endotracheal sample (if intubated) will be taken every day up to and including 1 day (+2 days) following the last dose of study drug. The timing of the LD will determine the nasal swab and/or endotracheal sampling times. If the administration of the LD is in the morning, all nasal swabs and/or endotracheal samples will be taken before the morning doses. If the administration of the LD is in the afternoon, all nasal swabs and/or endotracheal samples will be taken before the afternoon doses but after the morning doses. In case of nostril bleeding or irritation during the collection of a mid-turbinate nasal swab, all subsequent nasal swabs will be performed on the contralateral nostril. In case mid-turbinate nasal swabs are collected at home, this should be documented in the eCOA. Wherever possible,

mid-turbinate nasal swabs should be collected by a trained study team member in an inpatient or outpatient (clinic visit) setting. Whenever mid-turbinate nasal swabs cannot be taken by a trained study team member, the subject (or the subject's spouse, partner, relative, or friend) should collect swab specimens after being trained by the investigator/study-site personnel.

- t. Leftover mid-turbinate nasal swabs may be used to explore biomarkers (eg proteins including cytokines) at the discretion of the sponsor.
- u. Mid-turbinate nasal swab (if non-intubated) or mid-turbinate nasal swab and endotracheal sample (if intubated) must be taken as close as possible to and before the LD on Day 1. If the screening mid-turbinate nasal swab or endotracheal sample was performed less than 8 hours prior to LD, the Day 1 predose sample does not need to be collected.

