1.4. Sample Size Justification

The primary endpoint in this study is the AUC of the RSV RNA \log_{10} viral load over 7 days (or up to 11 days if the dose duration is extended up to 10 days).

The primary hypothesis is a positive dose-response relationship for the AUC of active treatment regimens. The positive dose-response relationship assumes that dose regimens with higher exposure with respect to MD will have at least an equal or better effect on viral load. Therefore 2 contrasts will be tested at each of the interim analysis points and final analysis; a contrast with no difference between the 2 active regimens tested against placebo and a contrast with a positive linear dose-response relationship with respect to active regimens. With respect to multiple contrast testing, multiplicity will be controlled at the pre-specified (interim) alpha level by calculating adjusted p-values from the simulated distribution of the maximum or maximum absolute value of a multivariate t random vector (ie, using the correlation between the contrasts to optimally control for alpha).¹ The overall (family-wise) type 1 error rate of 2.5% (1-sided) will be adjusted for multiple testing due to formal interim analyses using an O'Brien-Fleming alpha spending function with 3 sequential tests (2 interim, 1 final).⁵ As based on 10,000 simulations a sample size of 90 subjects randomized in a 1:1:1 ratio (placebo: low-dose ALS-008176: high-dose ALS-008176) will offer approximately 90% power to detect a positive dose-response relationship as defined assuming an effect size of 0.77 using Cohen's d (ie, the effect size expressed as the ratio of the standard deviation of the AUC) and approximately 80% power assuming an effect size of 0.67 (Cohen's d). Based on the results of the ALS-008176 RSV human challenge study, these effect sizes were considered plausible.⁶

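### The SAP has two conflicting rules for a Day 7 swab taken on Day 8 or 9, and it leaves open whether the supportive trapezoidal AUC0-7 ends at 144 h for every subject

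*SAP*

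**What the plan says.** **Sampling.** Footnote s of the protocol's Time and Events Schedule sets the swabs: "From Day 1 to Day 7 and on Day 10, Day 14, and Day 28, 1 mid-turbinate nasal swab". The schedule allows the Day 7 visit up to two days late. Under protocol 9.1.4, discharged subjects return as outpatients for it.

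**Visit allocation.** The SAP 2.1 table gives Day 7 the interval from day 7 to day 9 and names nasal swabs among the assessments covered. If two swabs fall in the interval, the one nearest the target day is used.

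**Primary endpoint.** SAP 4.2.3.1 says that, for post-baseline days, "the RSV RNA viral load result of the swab that was performed at that day will be used", counting the day of first treatment as Day 1. It gives no window. The model code in SAP 4.2.3.2 selects analysis visits 2 to 7.

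**Trapezoidal AUC0-7.** SAP 4.2.3.1 describes this as "based on planned days of sampling (Baseline visit up till/including Day 7 visit". In the formula, the time at which each post-baseline sample is collected "is the time in hours post baseline". The primary-endpoint rules apply first, then interpolation of gaps and carry-forward of the last value. SAP 4.2.3.2 calls the analysis supportive.

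**Later AUCs.** SAP Table 1 forms AUC0-10 by adding 3/2 times the sum of the Day 7 and Day 10 values to AUC0-7. AUC0-14 then adds 4/2 times the sum of the Day 10 and Day 14 values.

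**The concern.** Two things are unsettled for a subject whose only swab in the Day 7 window falls on Day 8 or 9.

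- **Primary model.** The window rule makes that swab the Day 7 observation. The exact-day rule leaves Day 7 missing, to be handled under missing at random. Two programmers could build different datasets for the confirmatory analysis and both follow the SAP.
- **Supportive trapezoid.** The AUC is a total, so a longer observation span gives a larger value for the same viral course. If actual collection times and the window are both used, subjects are not integrated over the same period.

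The trapezoidal value also appears to be the source of the AUC0-7 quartiles in SAP 4.6, which are used to display length of stay, functional recovery and clinical stability. If discharged subjects attend Day 7 later than inpatients are swabbed, early discharge would itself raise AUC0-7. The grouping variable would then depend partly on the outcome being displayed. That would not require any difference between arms.

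**Working it through.** **Plan's own figure.** The only stated number nearby is the power in SAP 1.4, and this point does not dispute it. The inputs are "a sample size of 90 subjects randomized in a 1:1:1 ratio", "The overall (family-wise) type 1 error rate of 2.5% (1-sided"), "approximately 90% power to detect a positive dose-response relationship as defined assuming an effect size of 0.77" and "approximately 80% power assuming an effect size of 0.67". I took the maximum of the plateau (-1, 0.5, 0.5) and linear (-1, 0, 1) contrasts, with correlation 1.5/√(1.5 × 2) = 0.866, 30 per arm, 87 degrees of freedom and both active arms at the stated effect. Simulation with 1,000,000 draws gives 91.1% and 81.9% at 0.025, and 90.5% and 81.0% at an assumed final O'Brien-Fleming level of 0.0231. The stated power reproduces.

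**Horizon of the primary contrast.** After the divisor of 4, the coded weights are 1 for each of Days 2 to 6 and 0.5 for Day 7. Adding 0.5 for baseline gives 5 × 1 + 0.5 + 0.5 = 6 days. The horizon is fixed at nominal days, whichever Day 7 rule applies.

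**Horizon of the trapezoid on actual hours.** Span = (study day - 1) × 24 h, taking swabs at the same clock time:
- Day 7: 144 h
- Day 8: 168 h
- Day 9: 192 h

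**One subject under each reading.** Assume baseline 6 log10, decline 0.5 log10/day, daily swabs to Day 6 (value 3.5) and then Day 9 (value 2.0). The area to Day 6 is (6 + 3.5)/2 × 5 = 23.75 log.day.

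| Reading | Last segment (log.day) | AUC (log.day) | AUC (log.h) |
|---|---|---|---|
| True course to 144 h | (3.5 + 3.0)/2 × 1 = 3.25 | 27.00 | 648 |
| Window, actual hours | (3.5 + 2.0)/2 × 3 = 8.25 | 32.00 | 768 |
| Window, nominal Day 7 | (3.5 + 2.0)/2 × 1 = 2.75 | 26.50 | 636 |
| Exact day, carried forward | 3.5 × 1 = 3.50 | 27.25 | 654 |

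Actual hours give 768/648 = +18.5%.

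**Range over assumed curves.** Effect of a Day 9 swab in place of a Day 7 swab, on actual hours:

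| Baseline (log10) | 0.3/day | 0.5/day | 0.7/day |
|---|---|---|---|
| 5 | +23.6% | +14.3% | +6.3% |
| 6 | +25.5% | +18.5% | +9.4% |

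In absolute terms this is +1.1 to +7.8 log.day for that subject. Placing the same Day 9 value at nominal Day 7 lowers AUC by only 0.3 to 0.7 log.day.

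**AUC0-10.** A flat load of 4 log10 gives 4 × 144 = 576 log.h for AUC0-7. The Table 1 increment is 3/2 × (4 + 4) = 12, in log.day. The sum of 588 matches neither consistent answer: 4 × 216 = 864 log.h or 4 × 9 = 36 log.day. On the actual-hours reading, a Day 9 swab also makes the segments cover 8 + 3 = 11 days, although Day 10 is 9 days after Day 1.

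**The case against.** The strongest reply is that the SAP can be read so that every trapezoid ends at 144 h. Planned sampling days suggest nominal times. The fixed 3-day and 4-day steps in Table 1 join coherently only to an AUC0-7 that stops at nominal Day 7. The trapezoid also inherits the exact-day rule, under which a Day 8 or 9 swab is not a Day 7 value. In the primary model, a rule written for the primary endpoint can be taken to override a general window.

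This stands in part. Unequal horizons are one permitted reading, not a certainty. It does not settle the matter, because the formula is in hours at sample collection, the window table names nasal swabs, and the model selects on the windowed variable.

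The reach is also limited. The trapezoid is supportive, the quartiles are exploratory, and SAP 4.2.4.2 tests AUC to Day 10 and Day 14 with the primary model rather than the Table 1 sums.

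A reader might infer a bias against the drug: treatment shortens stay, discharged subjects come late, and late swabs inflate AUC. Protocol 3.2 hopes for shorter stays and 11.3 anticipates a numerical trend. However, the documents give no figure for discharge by arm or for how late outpatients attend. The direction is unknown.

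**Conclusion.** The point holds as an ambiguity to be resolved before unblinding. The Day 7 input to the confirmatory model is contradictory, although its horizon is fixed and a late value placed at nominal Day 7 moves that subject's AUC by only about 0.3 to 0.7 log.day.

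For the supportive AUC, the horizon can be 144, 168 or 192 h if actual hours and the window are both used. A Day 9 swab then raises the affected subject's AUC by about 6 to 26%. These figures rest on assumed linear declines (baseline 5 to 6 log10, 0.3 to 0.7 log10/day). The consequence is added noise, with bias only if late swabs differ by arm, and possible distortion of the SAP 4.6 quartiles. The unit mismatch in AUC0-10 holds if AUC0-7 is computed in hours as its formula states; the overlap in time arises only on the actual-hours reading.

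A reader might also set one subject's shift against the powered effect, since 0.77 × an assumed SD of 6 to 9 log.day is 4.6 to 6.9 log.day. That comparison is not valid. Bias in an arm contrast is the shift times the between-arm difference in the late-swab proportion. With the 5.0 log.day example, an assumed 20-point difference gives 5.0 × 0.20 = 1.0 log.day, and reaching 4.6 would need 4.6/5.0 = 92 points. The documents give neither the SD nor the proportions.

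**What to change.** 1. **One Day 7 rule for both models.** For example, for Day 7 only, replace the exact-day bullet in SAP 4.2.3.1 with a reference to the SAP 2.1 window. The small downside is the 0.3 to 0.7 log.day shift when a Day 9 value stands at nominal Day 7 in the primary model.
2. **A common end for the trapezoid.** End every AUC0-7 at 144 h. If the Day 7 swab was taken on Day 8 or 9, interpolate to 144 h between the last swab at or before 144 h and that swab. In the worked example this gives 3.5 - 1.5 × 24/72 = 3.0 at 144 h and returns 648 log.h.
3. **One time unit.** Use it in AUC0-7, AUC0-10 and AUC0-14, and start the later segments from the 144 h value. In hours, the multipliers 3/2 and 4/2 become 36 and 48; the flat example then gives 576 + 36 × 8 = 864 log.h.

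The cost is a few sentences in the SAP and a few lines of code. No additional data collection is needed.

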4.2.3.2. Analysis Methods

Mean \log_{10} viral load values over time will be analyzed using a restricted maximum likelihood based repeated measures approach. Analyses will include the fixed, categorical effects of treatment, strata, visit, and treatment-by-visit interaction, as well as the continuous, fixed covariates of baseline \log_{10} viral load and baseline \log_{10} viral load by-visit interaction. An unstructured covariance structure will be selected. In case this model will not converge, the

following list of covariance structures will be applied and a selection will be based on the Akaike Information Criterion for those that do converge:

- Unstructured [UN]
- Ante-dependence [ANTE(1)]
- Heterogenous Toeplitz [TOEPH]
- Heterogeneous CS [CSH]
- Heterogeneous AR(1) [ARH(1)]
- Toeplitz [TOEP]

The Kenward-Roger approximation will be used to estimate denominator degrees of freedom.

The testing of the dose-response relation is based on the expectation that higher dose regimens will be at least as efficacious as lower dose regimens with respect to efficacy on the viral load over time. Therefore, two contrasts on the dose regimens have been selected that are consistent with this expectation: a contrast with no difference between the 2 active regimens tested against placebo and a contrast with a positive linear dose-response relationship with respect to active regimens. A multiple comparison approach will be taken testing the 2 contrasts combined versus placebo, adjusted for multiplicity.

The SAS mock code used to test the primary hypotheses will be as follows:

```
proc mixed data=viral_load;
  where avisitn in (2,3,4,5,6,7)
  class avisitn trt usubjid stratum;
  model logtiter = trt|avisitn stratum base|avisitn /ddfm=kr s;
  repeated avisitn/subject=usubjid type=un;
  lsmestimate trt*avisitn
  "Plateau" -4 2 2 -4 2 2 -4 2 2 -4 2 2 -4 2 2 -2 1 1,
  "Linear" -4 0 4 -4 0 4 -4 0 4 -4 0 4 -4 0 4 -2 0 2
  /divisor=4 adjust=simulate seed=3369 alpha=alpha* lower cl;
run;
```

The variable *trt* denotes the *placebo*, *low dose regimen*, and *high dose regimen* treatment groups, the *avisitn* variable denotes the swabbing visits at Days 2 through 7, and the *base* variable is the baseline log₁₀ viral load measured at Day 1.

The significance level of *alpha* (α^*) will have to be calculated based on the information fraction at the time of the test using the pre-specified O'Brien-Fleming (OBF) α spending function.

$$\alpha^*(t') = 2 - 2\phi(Z_{\alpha/2} / \sqrt{t'})$$

where $t' = n/N$, n is the ITT-i set size and N is the expected ITT-i set size at the end of study (=90) and ϕ denotes the standard normal cumulative distribution function.

The *lower* option is selected as the contrast needs to have a value below zero (ie, there needs to be a reduction in AUC comparing active treatment to placebo). In summary, a positive dose-response relationship will be concluded if based on this analysis for any of the two estimations the resulting adjusted p-value is lower than the associated OBF critical value.

The differences in the AUCs for active versus placebo will be derived using appropriate contrasts deriving least square mean differences, including the 95% 2-sided confidence intervals.

The individual AUC as calculated using the trapezoidal rule will be considered as a supportive analysis and will be analyzed using a linear model with AUC as a dependent variable and treatment group and stratum as fixed factors, and baseline log₁₀ viral load as fixed covariate. For this analysis no adjustments for multiplicity will be applied, that is the differences versus placebo will be estimated using appropriate contrasts with 95% confidence intervals.

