1.2. Trial Design

This is a randomized, double-blind, placebo-controlled, parallel-grouped, multicenter, dose-finding study of ALS-008176.

A target of approximately 90 subjects, ≥ 50 years of age who are hospitalized with RSV, will be randomly assigned in this study with 30 subjects planned per treatment regimen.

Subjects will be randomized in a 1:1:1 ratio to Regimen A, B, or C:

- Regimen A (placebo): a single LD (Dose 1) followed by 9 MDs (Doses 2 to 10) of matching placebo, administered twice daily.

- Regimen B (low-dose ALS-008176): a single 750 mg LD (Dose 1) followed by nine 250 mg MDs (Doses 2 to 10) of ALS-008176, administered twice daily.
- Regimen C (high-dose ALS-008176): a single 1,000 mg LD (Dose 1) followed by nine 500 mg MDs (Doses 2 to 10) of ALS-008176, administered twice daily.

The randomization will be balanced by using randomly permuted blocks and will be stratified by region (Japan versus non-Japan) and age (≥ 50 to < 65 years and ≥ 65 years).

The study will be conducted in 3 phases: a screening phase, a treatment phase from Day 1 to Day 5/6 (depending on the timing of the LD), and a follow-up phase for a total of 28 days post randomization. In the follow-up phase, subjects will have assessments completed at Day 7, Day 10, Day 14, and Day 28. Depending on discharge date, assessments will be completed either while hospitalized or during outpatient visits. For hospitalized subjects additional assessments are done as per the Time and Events Schedule. The duration of the subject's participation will be approximately 28 days, screening period not included.

Screening for eligible subjects will be performed as soon as possible following admission to the emergency room or hospitalization, such that subjects are randomized within 5 days of RSV symptom onset. Men or women ≥ 50 years of age diagnosed with RSV infection based on a polymerase chain reaction (PCR)-based diagnostic assay (with or without co-infection with another respiratory pathogen) who have been (or will be) admitted to the hospital and who have signed informed consent will be enrolled.

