2.3. Analysis sets

The analysis populations covered by this SAP will be:

Randomized Analysis set (RAND): All randomized subjects with a randomization date at or before the date of first intake of medication, or with a randomization date and a missing date for first medication intake.

Safety Set or All Subjects Treated set (AST): All subjects who received at least 1 dose of study drug, analyzed as treated.

Randomized or Treated (RT) set: All subjects who are in the Randomized Analysis Set (RAND) and/or the All Subjects Treated (AST) set.

Intention-To-Treat (ITT) set: All randomized subjects who receive at least 1 dose of study drug. Analyses on the ITT Set will be analyzed as randomized.

Intention-To-Treat-infected (ITT-i) set: All randomly assigned subjects who receive at least 1 dose of study drug and who have an RSV infection confirmed by a PCR-based assay at the central laboratory.

For the interim analysis: a subject is considered to have a confirmed infection with RSV if he/she has been diagnosed with RSV infection based on a PCR-based assay at the local laboratory and for which the RSV infection is confirmed by central laboratory or for which the result of the central laboratory testing is not available at cut-off.

Analyses on the ITT-i Set will be analyzed as randomized.

Per-Protocol (PP) Analysis set: All subjects in the ITT-i set who do not have protocol violations that may have an impact on the efficacy analysis. Decisions regarding which subjects are included in the PP set will be made before database lock on following criteria:

- Compliance: Subjects must have at most 1 missed dose. On the day of randomization at least one dose needs to be taken (so missed dose cannot be the first dose).
- The actual treatment must be the same as the planned treatment.
- No unblinding may have taken place during the study.
- Subjects will be excluded from the PP set if they have taken concomitant medications that may have affected the efficacy of the trial medication. Subjects will be excluded on a case by case basis using a list provided by clinical.
- Subjects may not violate inclusion criteria 3 or 4, nor exclusion criteria 1, 3, 8, 9, 10 or 13.

Analyses on the Per-Protocol set will be analyzed as randomized. Note that in the Per-Protocol set subjects will have been treated as randomized by definition.

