2.4. Statistical Methods

This SAP covers the statistical analysis for the final analysis. The interim analysis and IDMC analysis will be described in separate SAPs. Details of the single displays are described in the Data Presentation Specifications (DPS).

- The analysis population will be indicated in the titles of the displays.
- Unless stated otherwise, all results will be presented per treatment group. Tables on subject disposition, exposure, demographic data and baseline disease characteristics will include a ‘Total’ group, pooling all subjects. Tables on safety will include a “ALS-008176” group.
- Listings will be presented by treatment group and ordered by subject number and time point (if applicable).
- All outputs should be self-explanatory and therefore appropriate footnotes will be provided to clarify the contents of each listing, table or graph.
- In case the X-axis of a graph shows a time component, the distances between the time points will be proportional (not equidistant). Furthermore, when statistics are joined over time by a line, the actual statistics will be depicted by means of a symbol.
- Unless specified otherwise, continuous parameters will be summarized using the following statistics: number of observations, mean, standard deviation, minimum, median and maximum. The mean and median will be presented with one decimal place, while the standard deviation with two decimal places more than the decimal places of the raw data. The minimum and maximum will be presented to the same number of decimal places as the raw data.
- RSV RNA viral load mentioned in this document refers to the RSV RNA viral load qRT-PCR from nasal swab, unless otherwise stated.

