3. INTERIM ANALYSIS AND DATA MONITORING COMMITTEE REVIEW

The IDMC will review the safety data initially after approximately 12 subjects have completed treatment and when approximately 12 Japanese subjects have completed treatment to assess that treatment may safely continue in each arm. A separate SAP will be written that provides details on the data package for this purpose. Details on operational characteristics will be provided in the IDMC Charter.

In addition, a maximum of 2 interim analyses are planned to assess the primary endpoint for early superiority and futility. The first interim analysis will be performed when at least 45 subjects have been randomized, preferably after the end of a hemispheric RSV season. Up to the final database lock, the study team will remain blinded to the results. Details on operational characteristics will be provided in the interim analysis charter. An Interim Analysis SAP will be written that describes this formal interim analysis, focusing on the rules of futility, early superiority and sample size recalculation.

This interim analysis will be based on the subjects randomized up to that timepoint in the ITT-i Set.

The following situations will be considered based on the results of the primary analysis at this stage: that the study is considered futile; that superiority can be concluded (based on an O'Brien-Fleming alpha spending function); that the study is considered underpowered; or that the study should continue unchanged. In the case of the (unbinding) futility boundary or the superiority boundary being crossed, the IDMC will recommend early termination to the Sponsor Committee. If the study is considered underpowered, a sample size increase may be suggested to a maximum of 180 subjects. This blinded sample size calculation will take the residual error variance into account of the primary analysis model.

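### The SAP sets the primary test's significance level to the cumulative O'Brien-Fleming alpha, with N printed as 90, so the promised one-sided 2.5% is not kept once interims are done

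*SAP*

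**What the plan says.** SAP 4.2.1.1 sets a one-sided family-wise error of 2.5% that "will be adjusted for multiple testing due to formal interim analyses", using an O'Brien-Fleming spending function with two interim tests and one final test.

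SAP 4.2.3.2 puts this into practice. The significance level alpha* is passed to the SAS test call and "will have to be calculated based on the information fraction at the time of the test". The formula is alpha*(t') = 2 − 2Φ(Z_{α/2}/√t'), with t' = n/N, n the current ITT-i size, and N "is the expected ITT-i set size at the end of study (=90"). A positive dose-response is concluded if, for either contrast, "the resulting adjusted p-value is lower than the associated OBF critical value".

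Three other places bear on this:
- SAP 3 places the first interim at 45 or more randomised subjects and says that if the study looks underpowered "a sample size increase may be suggested to a maximum of 180 subjects". It leaves futility, early superiority and sample-size recalculation to a separate Interim Analysis SAP.
- SAP 1.2 gives "A target of approximately 90 subjects" as the number to be randomised. SAP 2.3 limits the ITT-i set to treated subjects "who have an RSV infection confirmed by a PCR-based assay at the central laboratory".
- SAP 2.4 states: "This SAP covers the statistical analysis for the final analysis".

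**The concern.** The printed formula is the Lan-DeMets O'Brien-Fleming function. It returns the total alpha that may have been spent by information fraction t'. The nominal level at a look after the first must be lower, because earlier looks have used part of that total. The SAP has no step that subtracts spent alpha or solves for a boundary. As written, a final look at n = 90 has t' = 1 and uses the full 2.5% even when one or two interims have already been taken.

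The fixed N adds two problems. If the sample size is raised and N stays at 90, t' exceeds 1 and alpha* exceeds 2.5%. If central confirmation leaves the ITT-i set below 90, t' stays below 1 at the final analysis and some alpha is never released.

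The α inside the formula is also not defined beside it. What is at stake is the rule for declaring the primary hypothesis met.

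**Working it through.** **Inputs.** One-sided α = 0.025 and three looks (SAP 4.2.1.1); the alpha* formula and N = 90 (SAP 4.2.3.2); first interim at 45 or more and maximum size 180 (SAP 3); 30 per arm, d = 0.77 or 0.67 (SAP 1.4). Assumptions: α = 0.025 in the formula, so Z_{0.0125} = 2.2414; second interim at 67.5, with other times shown, because the documents do not fix it; looks correlated √(n_i/n_j); normal theory.

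**The plan's own figure.** SAP 1.4 states about 90% power at d = 0.77 and about 80% at d = 0.67. Simulating the two-contrast test (contrast correlation 0.866) with correctly derived boundaries, three looks and both active arms at d gives 90.5% and 81.1%. The stated power therefore reproduces under correct incremental spending.

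**Printed levels.** alpha* = 2 − 2Φ(2.2414/√(n/90)):

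| n | 45 | 67.5 | 81 | 90 | 100 | 120 | 150 | 180 |
|---|---|---|---|---|---|---|---|---|
| alpha* | 0.00153 | 0.00965 | 0.0181 | 0.0250 | 0.0335 | 0.0522 | 0.0825 | 0.1130 |

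**Correct nominal levels, N = 90**, solved so that P(any rejection by look k) equals the cumulative spend at look k:
- looks 45/90: 0.00153 and 0.0245 (printed rule: 0.00153 and 0.0250);
- looks 45/67.5/90: 0.00153, 0.00916 and 0.0220 (printed rule: 0.00153, 0.00965 and 0.0250).

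**Overall one-sided error of the printed rule**, 1 − P(no look rejects), final n = 90:

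| Looks | Error |
|---|---|
| 90 only | 2.50% |
| 45/90 | 2.55% |
| 45/60/90 | 2.70% |
| 45/67.5/90 | 2.79% |
| 45/80/90 | 2.90% |
| 60/85/90 | 2.98% |

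Simulating the maximum of the two contrasts (4 million trials) gave 2.56% for 45/90 and 2.80% for 45/67.5/90.

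**Final n = 180, three treatments of N:**

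| Looks | N = 90 throughout | N = 90 at interims, t' = 1 at final only | N = 180 throughout |
|---|---|---|---|
| 45/180 | 11.3% | 2.6% | 2.50% |
| 45/67.5/180 | 11.6% | 3.2% | 2.51% |
| 45/90/180 | 12.0% | 4.2% | 2.55% |

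A second look at 135 with N = 90 throughout gives 12.8%. Smaller increases also matter: with interims at 45 and 67.5 and N = 90, overall error is about 3.6% at n = 100, 5.5% at 120 and 8.6% at 150. The middle column shows that a cap alone does not restore 2.5%.

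**Final ITT-i below 90.** Assume 10% unconfirmed, so n = 81 (27 per arm) and t' = 0.9. The final level is 0.0181 and overall error is 1.9% (45/81) to 2.1% (45/67.5/81). Power at the final look only, with both active arms at d and standard errors √(1.5/27) for plateau and √(2/27) for linear:

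| Final level | d = 0.77 | d = 0.67 |
|---|---|---|
| 0.0181 (printed) | 86.1% | 74.7% |
| 0.0220 | 87.7% | 77.2% |
| 0.0231 (re-derived for 45/67.5/81 with t' = 1) | 88.2% | 77.8% |

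The loss against the re-derived boundary is about 2.1 and 3.1 points.

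**The case against.** The text can be read charitably. It names a spending function, which is cumulative by definition, and cites the discrete sequential boundaries paper. The decision rule refers to an O'Brien-Fleming critical value, which could mean a properly solved boundary. N is defined as the expected ITT-i size, so a statistician could replace 90 once the target changes, and t' = 2 is not an information fraction. The 11% to 12% figure then arises only from misusing the definition. Sample-size rules belong to the Interim Analysis SAP, which is not among the documents. At n = 90 the excess is at most about half a point, in a Phase 2b dose-finding study with a viral-load endpoint. Below 90 the rule is conservative, and the 10% unconfirmed rate is not a figure from the documents.

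Much of this limits the size of the problem, and the n = 180 result should be read as conditional. It does not remove the defect. The only level the SAP defines is alpha*; it is called the significance level and passed to the test code, so a derived boundary has to be supplied from outside the text. N is printed as 90 with no update rule, while the same SAP allows 180. The final test is governed by this SAP, whatever the interim document says.

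**Conclusion.** The concern holds: as written, the rule does not keep the one-sided 2.5% promised in SAP 4.2.1.1 when interims are done.

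- At n = 90 the excess is small: none without an interim, 0.05 points with one at 45, about 0.2 to 0.4 points with two when the first is at 45, and about 0.5 points for looks as late as 60 and 85.
- It becomes large only if the sample size is raised and N is left at 90.
- Below 90 the error is kept, but power is given away.

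These figures rest on α = 0.025 in the formula and on the stated look times. If α were taken as 0.05 with the one-sided option in the code, the final level would be 5.0% at n = 90 and 16.6% at n = 180 before any interim, which is why α needs to be printed. The unseen Interim Analysis SAP may settle part of this. The point should be fixed before the first unblinded look.

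**What to change.** In SAP 4.2.3.2:
1. State α = 0.025 in the formula, and that alpha*(t') is cumulative and capped at 0.025.
2. State that the nominal boundary at each look is derived from the alpha increment and the joint distribution of the looks, for example 0.00153/0.00916/0.0220 for looks at 45/67.5/90, and that the adjusted p-value is compared with that boundary.
3. State that N is the currently planned ITT-i size, updated after any sample-size increase with alpha already spent held fixed.
4. State that t' = 1 at the final analysis whatever the final n.

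Use the same wording in the Interim Analysis SAP. The cost is a few lines of text and a slightly stricter final boundary when interims are done: 0.0245 with one at 45, or about 0.022 with two, instead of 0.025. The power stated in SAP 1.4 already reproduces with such boundaries, so the sample size need not change.
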